11 STUDY COMPLETION AND REMUNERATION

At the last scheduled protocol visit a study completion form will be completed, which requires the signatures of both the participant and the investigator. Participants will also be provided with a letter of appreciation.

Once their involvement in the study is complete, participants will be informed about receiving feedback following study completion in the Letter of Appreciation.

Participant remuneration will be provided at the end of their study involvement.

12 STATISTICAL ANALYSIS AND DATA MANAGEMENT

12.1 STATISTICAL ANALYSIS

All data will be analyzed by CORE at the University of Waterloo. Unmasked data analysis will be conducted using Statistica 10, Statsoft or other suitable software. Descriptive statistics will be provided on demographic data (age, gender, refractive error distribution, etc.). Table 7 lists the primary and other outcome variables and anticipated statistical procedures.

Visual acuity results will be converted to LogMAR for analysis purposes.

Comparisons will be made between the study lenses for the variables measured at the 1 month visits. Additionally the subjective ratings completed on days 7, 14 and 28 of each phase will be compared. A binomial test will be used to analyze the results for the count data of subjective preferences and experience responses. Where relevant, the number of “neither agree or disagree” responses will be evenly distributed to the two options on the basis they would be equally likely to choose either.

Because of the phenomenon of binocular summation, binocular visual acuity will be analysed, not right eye data. For other variables, such as lens fit, the right eye data will be reported and compared.

Where appropriate, such as for lens orientation, data may be presented as both mean and as counts by 'bucket' groups.

Table 7: Statistical procedures

Variable	Analysis	Statistical test
Ratings: Likert & Preference	Comparison between study days and/or between contact lenses per time point.	Freidman ANOVA Wilcoxon matched pairs test
Ratings: numerical ratings Biomicroscopy	Comparison between study days and/or between contact lenses per time point.	Freidman ANOVA Wilcoxon matched pairs test RMANOVA
Demographics Lens fit variables	Descriptive stats	One or more: mean, median*, mode, standard deviation, minimum, maximum, frequency count

* For non-parametric data only

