5.2 STUDY POPULATION

5.2.1 SAMPLE SIZE CALCULATION

The sample size was calculated using the end of month subjective ratings for 'lens handling for insertion' from a previous study.

In order to detect a mean difference of 0.7 units on the 0 to 10 scale for the end of month ratings of 'lens handling for insertion', using a standard deviation of 1.7 with 80% power and alpha 0.05 in a two-tailed t-test, a minimum sample size of 49 participants is recommended. To account for dropout, up to 60 participants may be randomized and dispensed with study product in total, with the target of at least 49 completing the study.

[figure not shown]

Figure 1: Sample size calculation graph

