5.4.10 VISIT 2-2, 1 MONTH FOLLOW-UP PAIR #2

This visit will occur on day 29-31 (inclusive) after the pair #2 lenses have been dispensed following visit 2-1.

Repeat steps 1-9 as listed for visit 1-2.

Participants will also complete preference questionnaires to compare the two study lens pairs.

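### Splitting neutral answers evenly before the binomial test makes that test too conservative, increasingly so as neutrals rise, and an odd neutral count has no rule

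*Combined protocol and SAP*

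**What the plan says.** Section 12.1 states: "A binomial test will be used to analyze the results for the count data of subjective preferences and experience responses". The next sentence, which opens "Where relevant, the number of", takes the responses in the neutral agree/disagree category and says these "responses will be evenly distributed to the two options on the basis they would be equally likely to choose either". It gives no rule for an odd number of neutrals and no analysis without them. It also states no null proportion or significance level for this test.

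Section 5.4.10 shows where the head-to-head data arise, at visit 2-2: "Participants will also complete preference questionnaires to compare the two study lens pairs". Section 5.2.1 sets the numbers: "up to 60 participants may be randomized and dispensed with study product in total, with the target of at least 49 completing the study". Table 7 assigns Friedman and Wilcoxon tests to Likert and preference ratings and does not list the binomial test.

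**The concern.** The plan's reason for the split is that a neutral participant would be as likely to pick one option as the other. That may justify a descriptive share over all participants. It does not turn a fixed allocation into independent random observations. Half of the neutrals are placed on each side with certainty, so they add to the test's sample size but nothing to its variability.

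Two things are at stake for these secondary results. On items with many neutral answers, a real preference can be missed, and a null result is hard to read because the actual significance level depends on the neutral share. With an odd neutral count, an unstated rounding choice, made after the data are seen, can decide whether an item is significant.

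**Working it through.** **Inputs from the plan.** Target of 49 completers and at most 60 randomized (Section 5.2.1); binomial test with an even split (Section 12.1).

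**Assumptions, because the plan gives no figures for this test.** Null proportion 0.5, two-sided 0.05, neutral share q from 5 to 50%, and a true preference of 70:30 among those who choose. The last is varied under the objection.

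**The plan's own figure.** Section 5.2.1 gives a sample size only for the primary outcome: a difference of 0.7, SD 1.7, "with 80% power and alpha 0.05 in a two-tailed t-test". Read as a paired t-test, the noncentrality at n = 49 is (0.7/1.7)×√49 = 2.88. Power is 0.806 at n = 49 and 0.798 at n = 48, so 49 is reproduced. No size or power is stated for the binomial test.

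**Mechanism.** Let A be the number choosing option 1, T the number of neutrals, and X = A + T/2 the count that is tested.

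- Under the null, A given T is Bin(N−T, ½), so Var(X | T) = (N−T)/4.
- The binomial test on X of N assumes N/4.
- In large samples the true size is 2[1 − Φ(1.96/√(1−q))]. At q = 30%, 1.96/√0.7 = 2.34, which gives 0.019. At 10, 20, 40 and 50% the size is 0.039, 0.028, 0.011 and 0.006.

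**Exact enumeration.** T ~ Bin(N, q) and A | T ~ Bin(N−T, π), with π = 0.5 for size and 0.7 for power. An odd neutral goes to a random side. Entries are percentages, split / neutrals excluded.

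| Neutral share | Size, N = 49 | Power, N = 49 | Size, N = 60 | Power, N = 60 |
|---|---|---|---|---|
| 5% | 4.0 / 3.5 | 77 / 75 | – | – |
| 10% | 3.5 / 3.7 | 73 / 74 | 2.1 / 3.7 | 75 / 82 |
| 20% | 2.5 / 3.4 | 62 / 67 | 1.4 / 3.7 | 64 / 77 |
| 30% | 1.7 / 3.2 | 48 / 60 | 0.9 / 3.6 | 49 / 71 |
| 40% | 1.0 / 3.0 | 34 / 51 | 0.5 / 3.3 | 33 / 62 |
| 50% | 0.5 / 3.0 | 19 / 43 | – | – |

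Part of the contrast between the two N is discreteness: with no neutrals the exact size is 4.4% at N = 49 and 2.7% at N = 60. Averaging over N = 45 to 60 smooths this. The mean power loss from splitting is then 2, 4, 9.5, 16 and 23 points at 5, 10, 20, 30 and 40% neutral. At 5% it ranges from −2 to +7 points, so the split is sometimes slightly better. At 20% it is worse at every N in the range, by at least 3.8 points.

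**Example without rounding.** 21 v 8 with 20 neutral.

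- Excluded: 21 of 29, p = 0.024.
- Split: 31 of 49, p = 0.085.
- The lead is 13 both ways. In approximate z terms it is 13/√29 = 2.41 against 13/√49 = 1.86.

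**Odd counts.**

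- 24 v 10 with 15 neutral: seven go to each side and one is left. p = 0.044 if it goes to the leader (32 of 49), 0.060 if dropped (31 of 48) and 0.085 if it goes to the trailer (31 of 49). Excluded: 24 of 34, p = 0.024.
- 30 v 16 with 3 neutral: p = 0.044 or 0.085 after the split, against 0.054 excluded (30 of 46). Here the rounding can move p either way.
- At N = 49, 30% neutral and 70:30, the probability of significance is 0.521 if the odd neutral goes to the leader and 0.449 if to the trailer. Placement therefore decides the result in 0.521 − 0.449 = 7.2% of trials per item, and in 0.8% under the null.

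**Why only generally conservative.** At N = 49, giving the leftover to the leader yields a conditional size of 0.0595 with one neutral and 0.0541 with three. Averaged over neutral counts, that rule stayed at or below 0.047 at every share tried.

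**The case against.** Several points can be made for the plan.

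- **Only 70:30 is shown.** True, and the gap depends on it. At N = 49 with 20, 30 and 40% neutral, power excluded v split is 19.4 v 16.0%, 16.6 v 10.9% and 13.9 v 6.5% at 60:40. At 80:20 it is 97.3 v 96.0%, 94.7 v 90.0% and 90.2 v 77.6%. At 20–30% neutral the loss is then about 1 to 6 points rather than 5 to 12, and the 7.2% rounding figure falls to 3.3%. The size shrinks but the direction does not change.
- **Table 7 offers other tests.** A difference in ratings collected for both lenses may still appear under Wilcoxon. That does not correct the binomial p-values, and it may not help a preference item asked once at visit 2-2. The overlap between Table 7 and the binomial sentence is real and should be settled.
- **The two options may be agree and disagree rather than the two lenses.** The category wording allows this, and redaction prevents a check of the items. The variance argument is the same either way. Redaction may also explain part of why the covered items are not visible, so no weight is placed on that gap.
- **Splitting keeps everyone in the denominator, and conservatism is the safer error with no multiplicity control.** Excluding neutrals does change the question to preference among those who have one. But a level that drifts with the neutral share is not a controlled correction, and the all-participant share can be shown without a test.
- **Neutral shares may be low.** The documents do not say. If they are about 5–10%, little is lost at N = 49, although at N = 60 and 10% the loss is already 82 − 75 = 7 points.

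**Conclusion.** The concern holds. Applied as written, the rule gives p-values that are generally too large, because the test uses variance N/4 where (N−T)/4 is correct. Under the stated assumptions (70:30, two-sided 0.05, N = 45 to 60) the average power loss is 2 to 4 points at 5–10% neutral, 9.5 at 20%, 16 at 30% and 23 at 40%. It is smaller for weaker or stronger preferences at 20–30% neutral. The neutral share and the preference are assumptions; the variance result does not depend on them. Separately, the missing rule for an odd neutral count can decide significance.

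The scope is limited to secondary counts. The primary Day 28 handling rating and the sample size of 49 are untouched, and false positives are not inflated in general. The change should be made, but it does not threaten the main conclusion.

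**What to change.** Replace the even-split sentence in Section 12.1 with wording such as:

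> For items analysed as counts, an exact two-sided binomial (sign) test will be applied to participants who chose one of the two options. The number and percentage giving the neutral answer will be reported as a separate category beside the result.

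List the items this covers, so that it is clear which are tested as counts and which are ordinal ratings under Table 7; the Table 7 tests for ordinal ratings stay. An all-participant share with neutrals split may still be shown descriptively, without a p-value. Excluding neutrals also removes the odd-count problem.

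The cost is one sentence and a list, with no new data. The downside is that the test speaks only for those who expressed a choice, on a smaller denominator, so the neutral count must always appear with it. At 5–10% neutral and N = 49 the change gains little or nothing.

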3 OBJECTIVES

The objective of the study is to compare the handling and performance of Biofinity Toric Multifocal to Ultra Multifocal for Astigmatism.

The primary outcome variable for this study is:

1. Subjective at-home ratings of 'Lens handling for insertion', using a 0-10 scale, collected on Day 28.

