4 HYPOTHESIS

The null hypothesis is that there will be no difference between the subjective at-home ratings of 'Lens handling for insertion', collected on day 28 for each lens type.

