5 MATERIALS AND METHODS

5.1 STUDY DESIGN

5.1.1 OVERALL DESIGN

This is a prospective, randomized, participant masked, crossover, bilateral dispensing study conducted at CORE and seven other clinical practice sites in Canada and the USA. Each lens type will be worn for approximately one month. The lens prescription of each lens type will be optimized after 3-7 days before the one month wear period.

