5.1.2 RANDOMIZATION

A randomization schedule will be generated using a web-based program: (www.randomization.com). The final study randomization schedule will be generated by CORE's Database Administrator and provided to the research assistants at each site for the study.

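### The Day 28 primary comparison of lenses in this two-phase crossover is planned without a period term, and no single primary test is named

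*Combined protocol and SAP*

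**What the plan says.** Section 5.1.1 describes a "prospective, randomized, participant masked, crossover, bilateral dispensing study", and Table 3 in section 5.4 lays it out as Phase 1 and Phase 2. The primary outcome in section 3 is the insertion-handling rating, "using a 0-10 scale, collected on Day 28". The null hypothesis in section 4 compares these ratings, "collected on day 28 for each lens type", and mentions neither phase nor order.

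Section 12.1 states that "Table 7 lists the primary and other outcome variables and anticipated statistical procedures", so Table 7 governs the primary outcome. Its row for numerical ratings describes the analysis as "Comparison between study days and/or between contact lenses per time point" and gives the tests as "Freidman ANOVA Wilcoxon matched pairs test RMANOVA". The text adds that "Additionally the subjective ratings completed on days 7, 14 and 28 of each phase will be compared". Study day and lens are the only factors named. No section names a term for period, sequence or carryover.

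On allocation, section 5.1.2 says "A randomization schedule will be generated using a web-based program" and gives no ratio, blocking or stratification. Section 5.2.1 sizes the trial at 49 completers (difference 0.7, SD 1.7, 80% power, two-sided 0.05, t-test) and allows up to 60 to be randomised.

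**The concern.** In a two-period crossover, half the participants rate a given lens in Phase 1 and half in Phase 2. The outcome is a self-rating of a manual task, and by Phase 2 each participant has handled another study lens for a month, so ratings could drift between phases whichever lens is worn.

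A comparison that ignores phase then suffers in two ways:

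- The shift enters the within-participant differences with opposite sign in the two sequences. It inflates their SD and costs power.
- If completers divide unevenly between sequences, part of the shift is carried into the lens estimate, in either direction.

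As listed, Wilcoxon matched pairs and Friedman cannot carry a period term. RMANOVA could, but none is specified for it. A smaller, related gap is that Table 7 does not say which test is primary at Day 28.

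**Working it through.** **Inputs.** Difference d = 0.7, SD = 1.7, two-sided alpha 0.05, 80% power, 49 completers, up to 60 randomised (section 5.2.1). The period shift P and the sequence split are not in the documents, so both are varied as assumptions.

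**1. Reproduce the plan's figure.** Paired t-test, noncentral t, SE = 1.7/√n: power is 79.8% at n = 48 and 80.6% at n = 49. The stated 49 is therefore a paired calculation with 1.7 as the SD of within-participant differences. A two-sample reading would need 93 per group.

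**2. Add a period term.** The lens effect is the mean of the two sequence-specific mean differences, with SE = (1.7/2)·√(1/n₁ + 1/n₂) and n − 2 degrees of freedom. At 25:24 the SE is 0.243 and power is 80.6%. The smallest adequate n is still 49.

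**3. Effect of omitting it, near balance.** With shift P, the differences centre on 0.7 − P in one sequence and 0.7 + P in the other. Their pooled SD becomes √(1.7² + P²·(1 − ((n₁ − n₂)/n)²)); at 25:24 and P = 1.0 this is √(2.89 + 0.9996) = 1.97. Simulation with 100,000 runs per cell and 1.7 excluding the shift (the range covers both directions of imbalance):

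| Shift P | Unadjusted power, 25:24 or 24:25 | With period term |
|---|---|---|
| 0.1 | 80.5-80.7% | 80.4-80.8% |
| 0.25 | 79.5-80.7% | 80.4-80.8% |
| 0.5 | 77.0-79.3% | 80.4-80.8% |
| 1.0 | 67.6-73.7% | 80.4-80.8% |

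**4. Uneven completers.** The unadjusted estimate moves by P·(n₁ − n₂)/n. At 29:20 the factor is 9/49 = 0.184, giving 0.05, 0.09 and 0.18 points for P = 0.25, 0.5 and 1.0. If allocation is unblocked, the chance of a split at least this uneven is 2·P(Bin(49, 0.5) ≥ 29) = 25%. Given that split, unadjusted type I error is about 5.7% at P = 0.5 and 6.5% at P = 1.0, against about 5% adjusted.

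**5. Averaged over simple random allocation.** The mean unadjusted estimate is 0.70 and type I error is 4.9-5.1%. Unadjusted against adjusted power:

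| Shift P | Unadjusted | Adjusted |
|---|---|---|
| 0 | 80.7% | 79.8% |
| 0.25 | 79.6% | 79.6% |
| 0.5 | 77.1% | 79.6% |
| 1.0 | 68.1% | 79.6% |

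**6. If 1.7 already contains the shift.** The residual SD is √(1.7² − P²) = 1.682, 1.625 and 1.375 for P = 0.25, 0.5 and 1.0. Near balance, unadjusted power is 80.3-81.5%, 80.6-82.7% and 83.0-87.5%; adjusted power is 81.4-81.5%, 84.0-84.1% and 93.6-93.7%.

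**7. Choice of test.** Reporting the smaller p-value of the paired t (identical to RMANOVA for two lenses) and Wilcoxon gives type I error of about 5.3-5.8% in 20,000 simulated null trials.

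**The case against.** The strongest reply is that the loss is hypothetical. No document gives a period shift. Participants must have worn soft lenses for at least three months (section 5.2.3), and the rating comes at Day 28, so a large learning effect is less likely. The worst figures need a shift of 1.0, larger than the 0.7 the trial seeks to detect. The SD comes from a previous study; if it was taken from raw crossover differences, it already contains any similar shift and planned power is kept. Adjustment also has a price: under random allocation with no shift it lowers power from 80.7% to 79.8%, and it only breaks even at a shift of 0.25. Finally, RMANOVA can include a period factor, so the plan is silent on adjustment and does not rule it out. On this view the unnamed primary test is the clearer defect.

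Most of this stands, and it limits the weight of the point: there is no systematic bias, average type I error is held, and small shifts cost almost nothing. It does not remove the point. Habitual wear and late rating do not exclude a shift, and the documents do not settle what the 1.7 contains. Balance among completers is not assured either, because no blocking is stated and up to 11 of 60 may drop out. Silence on the RMANOVA factors leaves the primary analysis without the term that the design calls for. The same amendment also settles which test is primary.

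**Conclusion.** The concern holds. The plan names no period or sequence term for the primary Day 28 comparison of a two-phase randomised crossover. This should be corrected, but as an inexpensive gain in precision and protection against chance imbalance, not as a threat to validity.

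Near balance, and with 1.7 excluding the shift, the cost in power is about one percentage point or less for shifts up to 0.25, roughly 1 to 4 points at 0.5, and 7 to 13 points at 1.0. At a 29:20 split the lens estimate moves by 0.05 to 0.18 points over shifts of 0.25 to 1.0. If 1.7 already includes the shift, planned power is kept and the period term only adds to it. All of this rests on assumed shifts and approximately normal differences. Confidence in the practical size is therefore medium, although the omission itself is plain from the text.

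**What to change.** In section 12.1 and Table 7, state one primary analysis, for example:

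> Primary analysis: Day 28 rating of lens handling for insertion, in participants with Day 28 ratings for both lenses; linear model with lens, period and sequence as fixed effects and participant as random effect (n − 2 degrees of freedom for the lens effect); two-sided alpha 0.05; lens difference with 95% CI.

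Name Wilcoxon matched pairs as a sensitivity analysis and keep Friedman for comparisons across days 7, 14 and 28.

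The cost is wording and one degree of freedom. Restricting to complete pairs keeps the analysed set the same as for a paired test. With no shift, power is 80.6% with or without the term at 25:24. Adjusted power falls to 79.2% at 29:20 and 76.7% at 32:17 (4% chance of a split at least that uneven if unblocked), against 80.6% unadjusted. The target of 49 can stay; if completers do split about 29:20, 51 of them (30:21) bring adjusted power to 81.0%, within the 60 who may be randomised. On simulated bounded 0-10 integer scores with 6-44% at the ceiling, the model held type I error at 4.8-5.1%.

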12.2 DATA MANAGEMENT

Data will be collected and written on paper forms which will be provided to each site by CORE. Each external site will email scanned forms to a designated person at CORE who will file the forms into pre-assigned binders and pass these binders to the data entry team. Data will be entered into a REDCap database developed and tested specifically for this study and accessible only to trained, authorised users. A data management plan will be developed to describe the data handling in more detail, including the personnel involved.

Data from this study will be retained by CORE for a minimum of 25 years on a password-protected server. After 25 years, data will be disposed of in accordance with the guidelines laid out by the University of Waterloo. More details regarding storage procedures are provided in section 15.7 and also in CORE SOP014 Clinical data management.

At the completion of the study CORE will provide a copy of the study data to the sponsor when requested. Data will typically be sent using a secure file share system operated by the University of Waterloo called Sendit which uses 128bit (or 256bit) SSL encryption. This system provides a secure way to transfer files when email is not appropriate, whether because of file size, file type or concerns over security. Sendit includes features such as password protection, a restricted

time period for download, IP logging and email notification of download. Files may be encrypted prior to transmission at the request of the sponsor. Using this method means that data files are only stored on University of Waterloo servers during the transfer.

12.3 COMMENTS ON SOURCE DOCUMENTS

Data analysis will not be conducted on comments which have been recorded in the source documents. Only relevant and applicable comments will be included in the final report as deemed necessary by CORE's Lead Investigator.

13 PROTOCOL & OTHER TRAINING

All study personnel will be required to complete training prior to their involvement in the study. Records of training will be kept at CORE. This will include training by CORE on the study protocol, study procedures, informed consent procedures, and on the randomization and participant masking procedures, as well as training for Good Clinical Practice.

All site Principal Investigators and co-investigators will provide a scan of their license to practice optometry and evidence of professional indemnity insurance.

